9.4.2. Primary Endpoint(s)

The primary objective of this study is to evaluate the percentage of time with glucose values within target range (70 to 180 mg/dL, both inclusive) after 35 days of using the study titration

scheme with LY900014 treatment and degludec. Both actual and change from baseline will be derived and analyzed by the ANCOVA model as described in Section 9.4.1.

The primary analyses will be conducted based upon the CGM data collected for Visit 3 (baseline) and Visit 14 (endpoint), excluding data (if any) that are collected while patients are temporarily off Humalog during the lead-in period or temporarily off IP during the maintenance period.

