6.3. Measures to Minimize Bias: Randomization and Blinding

This is a single-group, open-label study.

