8.1. Efficacy Assessments

8.1.1. Primary Efficacy Assessments

The primary efficacy measure is the change from baseline in percentage of time with sensor glucose values between 70 and 180 mg/dL (both inclusive), from CGM use in the maintenance period.

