9.2. Sample Size Determination

Approximately 34 participants will be assigned to study treatment such that 30 evaluable participants will complete the maintenance period, assuming a 10% dropout rate.

The study is not strictly powered to demonstrate a statistically significant change from baseline in the primary endpoint (percentage of time with glucose within 70 to 180 mg/dL) because of the exploratory nature of the study.

Using a standard deviation of 12%, the sample will provide approximately 80% coverage probability that the half-width of the 95% confidence interval of the change from baseline in the primary endpoint falls within 4.93%.

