9.4.1. General Considerations

Unless otherwise specified, all efficacy and safety analyses will be conducted on the Treated Population. Unless otherwise noted, all tests will be conducted at a 2-sided alpha level of 0.05, and confidence intervals will be calculated at 95%, 2-sided. Comparison between baseline and

endpoints will be performed at the full significance level of 0.05. No multiplicity adjustment will be made. Baseline is defined as the last non-missing measurement at or before the treatment assignment (Visit 3) unless otherwise specified.

An analysis of covariance (ANCOVA) will be used to analyze continuous variables that are planned to be collected only for baseline and endpoint. The model will include baseline as a covariate.

A restricted-maximum-likelihood-based, mixed model repeated measures (MMRM) analysis will be used to analyze continuous longitudinal variables collected only at baseline and more than one scheduled post-baseline visits according to SoA in Section 1.3. All the longitudinal observations at each scheduled post-baseline visit will be included in the analysis. The model for the analysis of the primary efficacy endpoint will include the fixed class effect of visit, and the random effect of patient. An unstructured covariance structure will be used to model the within-patient errors. Significance tests will be based on least-squares (LS) means and Type III tests. SAS PROC MIXED will be used to perform the analysis. If this analysis fails to converge, the following covariance structures will be tested in order:

- Toeplitz with heterogeneity
- Autoregressive with heterogeneity
- Compound symmetry with heterogeneous variances
- Toeplitz
- Autoregressive
- Compound symmetry without heterogeneous variances

The first covariance structure that converges will be used. The Kenward-Roger approximation will be used to estimate denominator degrees of freedom. If the analysis still does not converge with Compound symmetry without heterogeneous variances, only summary statistics will be provided.

For continuous measures, summary statistics will include sample size, mean, standard deviation, median, minimum, and maximum for both the actual and the change from baseline measurements. Least-square (LS) means and standard errors derived from the analysis models will also be displayed for the actual and the change from baseline measurements.

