6.9. Efficacy Analyses

6.9.1. Primary Outcome and Methodology

The primary objective of this study is to evaluate the percentage of time with glucose values within target range (70 to 180 mg/dL, both inclusive) after 35 days of using the study titration scheme with LY900014 treatment and degludec. Both actual and change from baseline will be derived and analyzed by the ANCOVA model as described in Section 6.1.

The primary analyses will be conducted on the Treated Population based upon the CGM data collected for Visit 3 (baseline) and Visit 14 (endpoint), excluding data (if any) that are collected while patients are temporarily off Humalog during the lead-in period or temporarily off IP during the maintenance period. Comparison between baseline and endpoints will be performed at the full significance level of 0.05.

Derivation and analysis of primary endpoint (derived for 24-hour, daytime and nighttime and by-meal) and other CGM endpoints are described in Section 6.13.

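### The single-arm ANCOVA on baseline understates the standard error of mean time in range and of its change, so the primary 95% CI is too narrow and the 0.05 test rejects too often

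*Protocol*

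**What the plan says.** Protocol 6.3 gives the design: "This is a single-group, open-label study". For variables collected only at baseline and endpoint, Protocol 9.4.1 specifies an ANCOVA and adds: "The model will include baseline as a covariate". No other term is named. Protocol 9.4.2 applies this model to time in range ("Both actual and change from baseline will be derived and analyzed by the ANCOVA model as described in Section 9.4.1"), and SAP 6.9.1 repeats it: "Both actual and change from baseline will be derived and analyzed by the ANCOVA model as described in Section 6.1". Model-based LS means and standard errors are to be shown for both quantities.

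The inference is formal. Under Protocol 9.4.1, "all tests will be conducted at a 2-sided alpha level of 0.05, and confidence intervals will be calculated at 95%, 2-sided", and SAP 6.9.1 adds: "Comparison between baseline and endpoints will be performed at the full significance level of 0.05". SAP 6.3 restricts the ANCOVA to completers.

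The sample size (Protocol 9.2, SAP 5.2) rests on precision alone. With an SD of 12% and 30 evaluable participants, it claims "approximately 80% coverage probability that the half-width of the 95% confidence interval of the change from baseline in the primary endpoint falls within 4.93" percent. On which quantity is primary, Protocol 8.1.1 says: "The primary efficacy measure is the change from baseline in percentage of time with sensor glucose values between 70 and 180 mg/dL". Protocol Section 3 lists the maintenance-period percentage itself.

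The same ANCOVA is prescribed for insulin doses (SAP 6.9.2), HbA1c, fructosamine and 1,5-AG (SAP 6.9.3) and the continuous CGM variables (SAP 6.13).

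**The concern.** In a randomised trial, a baseline covariate corrects chance imbalance between arms and sharpens the contrast. Here there is no contrast between arms. The question is how far the mean moved from baseline, and the baseline mean is itself estimated from the same 30 or so people. An ANCOVA that takes baseline as given removes the variation explained by baseline from the standard error. That variation still moves the sample mean from one trial to the next.

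The headline interval and p-value would therefore look more precise than the data support. This matters particularly here because precision is the only justification given for the sample size.

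**Working it through.** **Inputs from the documents.** 30 evaluable participants, SD 12 points, two-sided 0.05 and 95% CI, one group, baseline as the only covariate.

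**Assumptions.** The documents give no baseline-endpoint correlation r and no separate SDs. I take r from 0.3 to 0.9, equal SDs at first, an SD of change of 12, normal data, and the LS mean evaluated at the sample mean baseline (the usual default; the documents name no other value).

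**1. The plan's own figure.** For a one-sample t interval on the raw change:

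- SE = 12/√30 = 2.191
- half-width at SD 12 = t(0.975, 29) × SE = 2.045 × 2.191 = 4.48
- 80%-assurance half-width = 4.48 × √(χ²(0.80, 29)/29) = 4.48 × √(35.14/29) = 4.93
- probability of a half-width of 4.93 or less = 0.799

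This matches Section 9.2.

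**2. What the ANCOVA reports.** Let X be baseline, Y the endpoint value, D = Y − X the change, and b the slope of Y on X. At the sample mean of X, the LS mean of Y is the raw mean of Y, with model SE √(MSE/n). Modelling D changes the slope to b − 1 but leaves the residuals, and so the SE, unchanged. Actual value and change therefore always receive the same SE. In one simulated data set of 30, both model SEs were 1.96, against raw SEs of 2.32 (actual) and 2.29 (change), with identical point estimates.

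**3. What the SE should contain.** With σ_e² the residual variance:

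- Var(mean Y) = σ_e²/n + b²·Var(X)/n
- Var(mean D) = σ_e²/n + (b − 1)²·Var(X)/n

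The ANCOVA drops the second term of each. It is right for the change only if b = 1 and for the actual value only if b = 0, so it can never be right for both.

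**4. Size with equal SDs.** Here b = r, and the ratio of model SE to true SE is √((1 + r)/2) for the change and √(1 − r²) for the actual value. The sample mean is independent of MSE, so the true error rate is P(|T₂₈| > 2.048 × ratio). For the change at r = 0.5: 2.048 × 0.866 = 1.774, which gives 8.7%. The half-width column is 2.048 × 2.191 × ratio.

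| r | SE ratio, change | Type I error, change | Half-width shown (correct: 4.48) | 80%-assurance half-width (plan: 4.93) | SE ratio, actual | Non-coverage, actual |
|---|---|---|---|---|---|---|
| 0.3 | 0.81 | 11.0% | 3.62 | 3.99 | 0.95 | 6.1% |
| 0.5 | 0.87 | 8.7% | 3.89 | 4.28 | 0.87 | 8.7% |
| 0.7 | 0.92 | 6.9% | 4.14 | 4.56 | 0.71 | 15.5% |
| 0.9 | 0.97 | 5.6% | 4.37 | 4.82 | 0.44 | 38% |

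Simulation with 200,000 trials per correlation agrees: type I error 11.0%, 8.8%, 7.0%, 5.7%; coverage for the actual value 94.1%, 91.3%, 84.5%, 62.0%. The paired t-test stayed between 4.9% and 5.1%.

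**5. Unequal SDs.** Let k be endpoint SD over baseline SD. The ratio for the change becomes k√(1 − r²)/√(1 + k² − 2rk). At r = 0.7 the type I error is 11.6% for k = 0.8, 6.9% for k = 1 and 5.4% for k = 1.2. Over r = 0.3 to 0.9 it ranges from 11.3% to 15.8% for k = 0.8 and from 5.0% to 8.5% for k = 1.2. It reaches nominal only where the slope is close to 1. The ratio for the actual value does not depend on k.

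**The case against.** The strongest reply is that the ANCOVA interval is valid for the mean conditional on the observed baselines. That is true, and the under-coverage arises only when the target is the wider population. But neither document states a conditional target, and a baseline-versus-endpoint test at 0.05 is naturally read as a statement about the population.

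Second, the study is exploratory, has no power target and no success threshold, and its hypotheses section states no formal null. This limits the consequences. It does not remove the plan's own commitment to a 0.05 test and 95% intervals.

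Third, n, mean and SD of the raw change are planned as summary statistics, so a reader could rebuild the correct interval. That is a real mitigation, but the named inferential analysis would still be the wrong one.

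Fourth, the size rests on a correlation and SDs that the documents do not give. This stands. For the change the error can be small: 5.6% at r = 0.9 with equal SDs, and about 5% if the slope is near 1. For the actual value no reference mean is specified, so the effect there is under-coverage, not false rejection.

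Fifth, Section 9.2 names no method. Reading 12% as a residual SD with 28 degrees of freedom gives 4.95 and a probability of 0.792, also roughly 80%. The t interval on the change fits better, but the mismatch with Section 9.2 is supporting evidence and not a separate defect.

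**Conclusion.** The concern holds. For inference about the population, the planned standard error omits the sampling variation of the baseline mean. It is never too large, and it cannot be right for both the actual value and the change. The point estimates are unaffected.

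With 30 evaluable participants and equal SDs, the nominal 5% test of change runs at 11.0% to 5.6% as the correlation rises from 0.3 to 0.9, and non-coverage for actual time in range rises from 6.1% to 38%. The two errors trade off: the correlations that make the change nearly valid make the interval for the actual value worst. The size depends on the assumed correlation and SD ratio; the direction does not. Because it affects the headline interval and p-value, and the remedy costs almost nothing, it should be corrected before analysis.

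**What to change.** In Protocol 9.4.1 and 9.4.2 and SAP 6.1, 6.2, 6.9.1 and 6.13:

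- Analyse change from baseline with an intercept-only model, that is, a paired t-test and a one-sample t interval.
- Report the mean endpoint value with its ordinary one-sample t interval.
- Alternatively, fit a repeated-measures model with Visit 3 and Visit 14 both as responses and take the visit contrast, which is equivalent with complete pairs.
- Make the same change for the other baseline-and-endpoint variables in SAP 6.9.2 and 6.9.3.
- If the ANCOVA is kept, use it only to describe how change depends on baseline.

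Two related inconsistencies can be settled in the same edit. Name change from baseline as the primary measure, as Protocol 8.1.1 and 9.2 already treat it. Remove the leftover text in Protocol 9.4.1 and SAP 6.1 and 6.2 that assigns an MMRM to the primary endpoint.

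The cost is wording and simpler code, with no new data. The interval widens to the precision that Section 9.2 promises: a half-width of 4.48 points at an SD of 12, instead of about 3.6 to 4.4.

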9.4.3. Secondary Endpoint(s)

Additional continuous secondary efficacy variables, as well as the change from baseline for these variables, will be analyzed by the MMRM or ANCOVA model as described in Section 9.4.1.

Relationships between ICR and TDD will be evaluated through regression lines (ICR versus 1/TDD) and compared with the “500 Rule,” which is currently used in clinical practice where ICR = 500/TDD (Section 2.1).

9.4.4. Exploratory Endpoints

Additional continuous exploratory efficacy variables, as well as the change from baseline for these variables, will be analyzed by the MMRM or ANCOVA model described in Section 9.4.1, unless otherwise specified.

Relationships between the following endpoints will be explored through regression lines (King et al. 2007a, 2007b).

- ISF and 1/TDD
- ICR and ISF
- TBD and weight

9.4.5. Other Safety Analyses

Safety measures will include AEs, vital signs, and treatment exposure. Events that are newly reported after the first dose of IP used or reported to worsen in severity from baseline (details will be described in SAP) will be considered TEAEs.

Analyses of AEs will be descriptive and include all data collected during the treatment period. AEs during the lead-in period and the safety follow-up period will be provided in a listing.

Serious AEs, AEs reported as the reason for discontinuation from the IP or study, and TEAEs will be summarized in tables using the Medical Dictionary for Regulatory Activities (MedDRA) Preferred Term sorted by decreasing frequency. Treatment-emergent AEs will also be summarized by preferred term sorted by decreasing frequency within the SOC for all TEAEs and by maximum severity. For events that are gender-specific (as defined by MedDRA), the denominator and computation of the percentage will include only patients from the given gender. The number and proportion of patients with at least 1 event for each type of event will also be summarized.

In addition, time in hypoglycemic ranges will be assessed by CGM analyses.

9.4.6. Other Analyses

Analysis details for additional exploratory endpoints will be described in the SAP.

9.5. Interim Analyses

No interim analyses are planned for this study. If an unplanned interim analysis is deemed necessary, the appropriate Lilly medical director, or designee, will be consulted to determine whether it is necessary to amend the protocol.

9.6. Data Monitoring Committee

No Data Monitoring Committee is planned for this study.

10. Supporting Documentation and Operational Considerations

10.1. Appendix 1: Regulatory, Ethical, and Study Oversight Considerations

10.1.1. Regulatory and Ethical Considerations

This study will be conducted in accordance with the protocol and with the following:

- Consensus ethical principles derived from international guidelines including the Declaration of Helsinki and Council for International Organizations of Medical Sciences (CIOMS) International Ethical Guidelines
- Applicable International Council for Harmonisation (ICH) Good Clinical Practice (GCP) Guidelines
- Applicable laws and regulations

The protocol, protocol amendments, ICF, Investigator Brochure, and other relevant documents (for example, advertisements) must be submitted to an IRB/IEC by the investigator and reviewed and approved by the IRB/IEC before the study is initiated.

Any amendments to the protocol will require IRB/IEC approval before implementation of changes made to the study design, except for changes necessary to eliminate an immediate hazard to study participants.

The investigator will be responsible for the following:

- Providing written summaries of the status of the study to the IRB/IEC annually or more frequently in accordance with the requirements, policies, and procedures established by the IRB/IEC
- Notifying the IRB/IEC of SAEs or other significant safety findings as required by IRB/IEC procedures
- Providing oversight of the conduct of the study at the site and adherence to requirements of 21 Code of Federal Regulations (CFR), ICH guidelines, the IRB/IEC, European regulation 536/2014 for clinical studies (if applicable), and all other applicable local regulations

Investigator sites are compensated for participation in the study as detailed in the clinical trial agreement

10.1.2. Financial Disclosure

Investigators and sub-investigators will provide the sponsor with sufficient, accurate financial information as requested to allow the sponsor to submit complete and accurate financial certification or disclosure statements to the appropriate regulatory authorities. Investigators are responsible for providing information on financial interests during the study and for 1 year after completion of the study.

10.1.3. Informed Consent Process

The investigator or his or her representative will explain the nature of the study, including the risks and benefits, to the participant and answer all questions regarding the study.

Participants must be informed that their participation is voluntary. Participants will be required to sign a statement of informed consent that meets the requirements of 21 CFR 50, local regulations, ICH guidelines, Health Insurance Portability and Accountability Act (HIPAA) requirements, where applicable, and the IRB/IEC or study center.

The medical record must include a statement that written informed consent was obtained before the participant was entered in the study and the date the written consent was obtained. The authorized person obtaining the informed consent must also sign the ICF.

Participants must be re-consented to the most current version of the ICF(s) during their participation in the study.

A copy of the ICF(s) must be provided to the participant and is kept on file.

10.1.4. Data Protection

Participants will be assigned a unique identifier by the sponsor. Any participant records, datasets or tissue samples that are transferred to the sponsor will contain the identifier only; participant names or any information which would make the participant identifiable will not be transferred.

The participant must be informed that his or her personal study-related data will be used by the sponsor in accordance with local data protection law. The level of disclosure must also be explained to the participant who will be required to give consent for their data to be used as described in the informed consent.

The participant must be informed that his or her medical records may be examined by Clinical Quality Assurance auditors or other authorized personnel appointed by the sponsor, by appropriate IRB/IEC members, and by inspectors from regulatory authorities.

10.1.5. Dissemination of Clinical Study Data

Reports

The sponsor will disclose a summary of study information, including tabular study results, on publicly available website where required by local law or regulation.

Data

The sponsor provides access to all individual participant data collected during the trial, after anonymization, with the exception of PK or genetic data. Data are available to request 6 months after the indication studied has been approved in the United States (US) and European Union (EU) and after the primary publication acceptance, whichever is later. No expiration date of data requests is currently set once data are made available.

Access is provided after a proposal has been approved by an independent review committee identified for this purpose and after receipt of a signed data sharing agreement. Data and documents, including the study protocol, statistical analysis plan, clinical study report, blank, or annotated case report forms, will be provided in a secure data sharing environment for up to 2 years per proposal.

For details on submitting a request, see the instructions provided at www.clinicalstudydatarequest.com.

10.1.6. Data Quality Assurance

- All participant data relating to the study will be recorded on printed or electronic CRF unless transmitted to the sponsor or designee electronically (for example, laboratory data). The investigator is responsible for verifying that data entries are accurate and correct by physically or electronically signing the CRF.
- The investigator must maintain accurate documentation (source data) that supports the information entered in the CRF.
- The investigator must permit study-related monitoring, audits, IRB/IEC review, and regulatory agency inspections and provide direct access to source data documents.
- Monitoring details describing strategy (for example, risk-based initiatives in operations and quality such as Risk Management and Mitigation Strategies and Analytical Risk-Based Monitoring), methods, responsibilities and requirements, including handling of noncompliance issues and monitoring techniques are provided in the Monitoring Plan.
- The sponsor or designee is responsible for the data management of this study including quality checking of the data.
- The sponsor assumes accountability for actions delegated to other individuals (for example, Contract Research Organizations).
- Study monitors will perform ongoing source data verification to confirm that data entered into the CRF by authorized site personnel are accurate, complete, and verifiable from source documents; that the safety and rights of participants are being protected; and that the study is being conducted in accordance with the currently approved protocol and any other study agreements, ICH GCP, and all applicable regulatory requirements.
- Records and documents, including signed ICFs, pertaining to the conduct of this study must be retained by the investigator for the period outlined in the Clinical Trial Agreement (CTA) unless local regulations or institutional policies require a longer retention period. No records may be destroyed during the retention period without the written approval of the sponsor. No records may be transferred to another location or party without written notification to the sponsor.
- In addition, Sponsor or its representatives will periodically check a sample of the participant data recorded against source documents at the study site. The study may be audited by Sponsor or its representatives, and/or regulatory agencies at any time. Investigators will be given notice before an audit occurs.

Data Capture System

The investigator is responsible for ensuring the accuracy, completeness, legibility, and timeliness of the data reported to the sponsor.

An electronic data capture system (EDC) will be used in this study for the collection of CRF data. The investigator maintains a separate source for the data entered by the investigator or designee into the sponsor-provided EDC system. The investigator is responsible for the identification of any data to be considered source and for the confirmation that data reported are accurate and complete by signing the CRF.

Data collected via the sponsor-provided data capture system will be stored at a single third-party. The investigator will have continuous access to the data during the study and until decommissioning of the data capture system. Before decommissioning, the investigator will receive an archival copy of pertinent data for retention.

Data managed by a central vendor, such as laboratory test data, will be stored electronically in the central vendor's database system and reports will be provided to the investigator for review and retention. Data will subsequently be transferred from the central vendor to the Sponsor data warehouse.

Data from complaint forms submitted to Sponsor will be encoded and stored in the global product complaint management system.

